The effect of a structured, home-based interview with a patient with a chronic illness on first-year medical students' patient-centredness: protocol for a randomised controlled trial.

19th October 2018

NCT03722810

[name], [name], [name], [name], [name]

Protocol v2b (English language only)

Abstract

Background

Doctors are regarded as professionals, and specific teaching on professional behaviour is considered important in many countries. For medical students, early patient contact experiences were found to be an important way of learning about professionalism, and learning activities promoting critical reflection were particularly effective. Medical students consider that patient-centredness is one of the most important aspects of medical professionalism, and the PPOS questionnaire has been used extensively in measuring the attitudes of medical students towards patient-centredness. The PPOS-D12 questionnaire is a validated German version of that questionnaire.

The study aim is to assess how a structured, in-depth, home-based interview with a patient with a chronic illness affects first-year medical students' patient-centredness.

Methods

In this randomised controlled trial, medical students who are in the first year of their studies at the University of Bern will be randomised to either seeing a patient with a chronic illness for a structured, in-depth interview in their own home (the intervention), or to reading an educational document that gives information about consultation skills (the sham comparator).

Students will complete the PPOS-D12 survey before and after the interventions, so that changes in their scores can be calculated, and the mean scores of the two groups compared. Secondary outcomes will be the effect of students' gender and prior exposure to chronic illness in the participant or her/his close relatives and friends on their PPOS-D12 scores. A nested study will measure the strength of association between the GP teachers' own levels of patient/doctor-centredness and changes in their students' levels over the year.

Discussion

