There have been more than 900 papers published that measure patient-centred care or one of its components [14]. However, only two measurement instruments for attitudes towards patient-centredness in undergraduate medical students have been identified: the Doctor Orientation Scale and the Patient-Practitioner Orientation Scale (PPOS); of these two, the PPOS has been used much more extensively [15]. The PPOS was developed in 1999 to measure the attitudes of medical students towards patient-centredness [16]. It differentiates between patient-centred versus doctor-centred or disease-centred orientation, measuring attitudes along 2 dimensions: 'sharing' and 'caring' [17]. It has been used to assess attitude changes towards patient-centredness in medical student cohorts as they progress through the clinical curriculum.

The PPOS is available in 13 languages. It has been translated into German and the degree of medical students' patient-centeredness assessed in 2 student samples in Freiburg, Germany and in Basel, Switzerland [18]. Construct validity was tested using factor analysis. Based on factor analysis and tests of internal consistency, a shortened version with 6 items for each of the 2 subscales "sharing" and "caring" was generated (PPOS-D12). PPOS-D12 (see English-language version at Appendix 1) was found to be a reliable instrument to assess patient-centeredness among medical students in German-speaking countries.

In a longitudinal survey of medical students' attitudes toward patient-centred care in Greece, students' attitudes were significantly less patient-centred at the end of their studies compared to the beginning of their clinical curricula (mean score in year 4: 3.96; mean score in year 6: 3.81; $P < 0.001$) [17]. In a South African study, medical students from all undergraduate six years took the PPOS survey. There was a decrease in mean scores (from 2.65 in first-year students to 2.25 in final-year students), with the most pronounced decrease in the first two years of study [15]. [19]. In a year-long study of resident physicians at a university hospital in Tokyo, PPOS scores reduced significantly over the year (mean score at start of year: 4.5, SD 0.48; mean score at end of year: 4.39, SD 0.51; change: -0.11, SD 0.42) [20].

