We have only identified one study that assessed the effect of an intervention on students' levels of patient-centredness. In this uncontrolled UK study, first-year dental undergraduates were given an attitudinal questionnaire to complete before and after their behavioural science course. No significant difference was found between their mean pre- and post-course PPOS scores (pre-course mean scores: 3.44 SD 0.33; post-course mean score: 3.37, SD 0.19; $P > 0.05$). We have found no controlled trials that test the effect of interventions on medical students' levels of patient-centredness, and no trials that look at the effect of early patient contact in the form of an unaccompanied visit to a patient in their home.

Aim of the study

The aim of this study is to assess how a structured, in-depth, home-based interview with a patient with a chronic illness affects first-year medical students' patient-centredness.

A nested study will assess whether the GP's level of patient/doctor-centredness affects changes in their student's level over the year.

Methods

Study setting

The study will take place in the Berner Institut für Hausarztmedizin (BIHAM) at the University of Bern, Switzerland, and a subset of the >700 General Practitioner (GP) teaching practices that are affiliated to it.

Study participants

The population will be medical students who are in the first year of their studies (their first Bachelor year) at the University of Bern, during their longitudinal placements in primary care. The GP teachers are family doctors that are accredited by BIHAM to take medical students.

Study design

This will be a randomised controlled trial. During their first Bachelor year, each medical student will spend a series of six half-days at the practice of a GP teacher that she/he has been allocated to. Students will be randomly assigned to either the intervention or the sham comparator which will take place during their last half-day in their practices. All students will complete an on-line version of the PPOS-D12 questionnaire at the start of the academic year and once more after the last half-day at their GP teachers' practices.

Intervention

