The intervention will be a structured in-depth interview with a patient with a chronic illness that has been chosen by the student's allocated GP teacher. These chronic diseases are the four conditions at the top of a list of diseases with high disability-adjusted life years (DALY) scores in Switzerland: ischemic heart disease, low back pain, major depressive disorder and COPD [21]. GP teachers who only see children are asked to choose a patient who has a chronic cardiac condition, a chronic lung disease, or another chronic illness that has a significant effect on the child's quality of life, the interview to be carried out at the child's home with one or both parents, and the child if she/he is old enough to take part in the interview.

GP teachers and students will be told that the students' intervention interviews need to be unaccompanied and at patients' own homes, but in justified, exceptional cases, and after consultation with a member of the research team, the interview may take place in the GP teacher's practice premises. The interview will be followed by a structured interview with the practice nurse and then a structured debriefing interview with the GP teacher.

Sham comparator

In the sham comparator, the student's the allocated GP teacher will give the student time to read a document that gives information about consultation skills, and asks questions that the student will need to discuss with the GP teacher. The document is designed to have real educational value, and to complement BIHAM's department-based consultation skills teaching. The use of this approach as the sham intervention is based on a study that found that a behavioural science course (including consultation skills teaching) had no effect on students' PPOS scores [19].

Data collection

At the start of the academic year (i.e. before the interventions), students will complete a SurveyMonkey questionnaire that asks for demographic information (gender, history of serious chronic illness in the participant, a friend or close relative, history of training or patient contact other than in medical school) and the PPOS D12 form.

At the end of their GP attachment (i.e. after the interventions), students will complete a SurveyMonkey questionnaire that asks whether they had the intervention or sham comparator or neither (and if neither, why), and the PPOS D12 form. Consent to use these data for research will also be requested.

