At the end of their students' attachments, their GP teachers will complete a SurveyMonkey questionnaire that asks them to complete the PPOS D12 form. Consent to use these data for research will also be requested.

Each of these questionnaires will ask for the participant's name, so that pre-intervention, post-intervention, and GP's data can be linked and compared.

Outcome measures

The primary outcome measure will be the change in students' PPOS-D12 scores from baseline (at the start of the academic year) to the end of their year-long primary care attachment.

Secondary outcomes will be the effect of students' gender, previous experience and prior exposure to chronic illness in the participant or her/his close relatives and friends on their PPOS-D12 scores

A nested study will measure the strength of association between the GP teachers' own levels of patient/doctor-centredness and changes in their students' levels over the year.

Development of the intervention

Following a literature review and discussion, RF, [name] and MH developed a patient interview pro-forma which was designed to identify patients' views on their illnesses, how it affects their lives in physical, psychological and social terms, and how their relationships with their GPs impacts on their lives. The sections of the interview pro-forma map across to Mead and Bower's conceptual framework of patient-centredness given above [22].

Six medical students who had been visiting their GP teachers for eight half-days per year since their first year of study agreed to pilot the intervention in November 2017. The GP teachers were asked to select a patient with a chronic illness for their students, and to organise 2.5-hour interviews, half of the students at the patients' home and in the other half in the teaching practices. Students were asked to use the questionnaire pro-forma. In addition, the students each had a 30-minute interview with a practice nurse to assess their perceptions of the effect of the illnesses on their patients, and finally a one-hour discussion with their GP teacher to reflect on their encounters with the patients, discuss their findings, and talk about any difficulties that may have arisen.

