- Students. In a tailored informed consent procedure, students will be given a 'high-level description' of the study objectives with only superficial information on the study interventions, as accepted by ethics committees in similar studies. They will be informed that they are randomised to one of two study groups, without revealing that one is an intervention and the other is a sham comparator. The aim of this is to minimise performance and other reporting biases.
- GP teachers. A similar approach will be taken with information for the GP teachers, so that they also have only a 'high-level' description of the study objectives.

Statistical analysis

Descriptive statistics will be used to describe the relationships between student demographics and PPOS scores. Mean pre- and post-test PPOS scores will be compared using paired *t* tests. Differences between PPOS scores in the intervention and control groups will be examined with unpaired *t* tests. For the nested study, GPs' PPOS scores and changes in their students' PPOS scores will be compared using paired *t* tests.

The sample size calculation for the primary outcome was based on reported mean reduction of 0.11 in the PPOS score over one year in a group without any intervention [20], and a mean increase of 0.05 in the intervention group. We therefore assumed a mean difference 0.16, with a standard deviation of 0.42. The study was designed with a 5% level of significance and a 90% power to reject the null hypothesis of equivalence between the two groups. To achieve this objective, 220 students would be required (110 for each group). Assuming a 20% drop-out, we therefore aimed to enrol a total of 275 students.

Discussion

This research will consider the effect of an in-depth, structured interview with a patient with a chronic illness on changes in first-year medical students' levels of patient-centredness. There is existing evidence that medical students' levels of patient-centredness reduce over their student years, and this study will contribute to an understanding of how this reduction can be minimised or reversed.

Strengths

To our knowledge, this is the first randomised controlled trial that has been designed to study the effect of an intervention on medical students' levels of patient-centredness. The intervention materials were carefully developed and piloted by GP teachers and medical students, and therefore grounded in their clinical and educational experience.

Limitations

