Although the research team will give participants information about the study in a presentation and in correspondence, there is a risk that fewer students than anticipated consent to take part in the study. While the researchers aim to blind participants to the nature of the comparison, i.e. that one intervention is the intervention and the other is a sham comparator, control intervention, participants may guess the researchers' intentions, and this may result in bias in their responses. The power calculations have been based on data from other published studies, but these may not be directly comparable to our own study. Our control intervention has been chosen because of evidence that teaching dental students about communication skills does not affect their levels of patient-centredness, but it is possible that our communication skills intervention will indeed have an effect the levels of our medical students' patient-centredness, and thus not be a truly inactive control.

Expected impact

One of the aims of BIHAM's clerkships in primary care is to shift the medical students' focus towards 'professionalism', and patient-centredness is an important aspect of professionalism. This study will assess whether a single in-depth structured interview with a patient, followed by a de-briefing interview with the patient's GP, can contribute to achieving this aim.

Quality assurance

The study may be monitored or audited in accordance with the current approved protocol, relevant regulations and standard operating procedures.

Confidentiality

The research team will ensure that the participants' anonymity is maintained. As soon as each student's pre- and post-intervention questionnaires have been matched with each other and those of their GP teachers, each participant will be identified only by a participant ID number on all study documents and any electronic database. All documents will be stored securely and only accessible by study staff and authorised personnel. Under no circumstances will the identifiers be made available to individuals outside the research team.

Dissemination

Results will be published in peer-reviewed scientific journals as well as by conference presentations. The researchers will publicise the project findings within their university and the Swiss health system, for example in newsletters, websites, meetings and local journal publications.

Funding

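### Secondary outcomes on three student factors are assigned descriptive statistics only: no difference or confidence interval is specified, and neither the score nor the question is named

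*Combined protocol and SAP*

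**What the plan says.** Methods, Outcome measures, names change from baseline as the primary outcome. It then states: "Secondary outcomes will be the effect of students' gender, previous experience and prior exposure to chronic illness", in the participant or in people close to them, on the students' PPOS-D12 scores. It does not say which score. The abstract has a shorter list without previous experience: "Secondary outcomes will be the effect of students' gender and prior exposure to chronic illness".

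Methods, Data collection, treats these factors as demographic information collected at the start of the year. Besides gender, the items are "history of serious chronic illness in the participant, a friend or close relative, history of training or patient contact" outside medical school.

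Methods, Statistical analysis, has one sentence that covers them: "Descriptive statistics will be used to describe the relationships between student demographics and PPOS scores". The t tests in that section compare pre with post scores, intervention with control, and, in the nested study, GPs' scores with changes in their students' scores. None is by student factor.

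**The concern.** Declaring the effect of a factor as an outcome promises an answer about size: how far apart the factor levels are, and how well that is known. A descriptive summary need not give either. If only group means are tabulated, a reader cannot tell a difference that the data support from one that they do not.

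Two further points are open:

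- **The score.** Baseline asks who starts out more patient-centred, final asks who ends so, and change asks who shifts over the year. Unless one is named, the score to emphasise can be picked after the results are known.
- **The question.** In a randomised trial, the effect of gender on the score could mean an association across all students. It could also mean that the intervention works differently in men and women. The two need different analyses, and the plan does not say which is meant.

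None of the factors is randomised, so the word *effect* also claims more than the design can show.

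**Working it through.** **1. Text side by side.**

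| Item | Outcome measures | Statistical analysis |
|---|---|---|
| Primary outcome | Change from baseline, named | Unpaired *t* test between arms |
| Student factors | Three factors, on scores not further defined | Descriptive statistics only |
| Nested study | Association with changes in students' levels | Paired *t* test |

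The student-factor row is the only one without a named comparison. It is also the only one that does not say change, although the rows on either side of it do.

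**2. Inputs for an illustration.** The plan gives no figure for the secondary outcomes, so there is none to reproduce. From Statistical analysis I take 220 students analysed (110 per arm; 275 × 0.8 = 220), SD 0.42 for change and a planned difference between arms of 0.16. I use 220 only as a head count; whether it delivers the stated power for the primary comparison is a separate matter. The factor splits are my assumption, because the documents give none.

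**3. Association (mean difference in change between two levels of a factor).** Half-width = 1.96 × SD × √(1/n₁ + 1/n₂).

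- 60:40 split (132 and 88): 1.96 × 0.42 × √(1/132 + 1/88) = 1.96 × 0.0578 = 0.113
- 80:20 split (176 and 44): 1.96 × 0.42 × √(1/176 + 1/44) = 1.96 × 0.0708 = 0.139
- Primary contrast, for scale (110 and 110): 1.96 × 0.42 × √(2/110) = 0.111

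An observed factor difference of 0.10 at a 60:40 split would therefore have an interval from 0.10 − 0.113 = −0.013 to 0.10 + 0.113 = 0.213. It includes zero, which group means alone would not show.

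**4. Effect modification (factor-by-arm interaction).** Assume the same split in both arms. The four cells then give half-width = 1.96 × SD × √(2/a + 2/b), where a and b are the numbers per arm at each level.

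- 60:40 (66 and 44 per arm): 1.96 × 0.42 × √(2/66 + 2/44) = 0.227
- 80:20 (88 and 22 per arm): 1.96 × 0.42 × √(2/88 + 2/22) = 0.278

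These are twice the values in step 3 and exceed 0.16, so which question is meant affects how much the trial can say.

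The SD comes from the cited study of resident physicians. The plan's own Limitations section says of its published inputs, "but these may not be directly comparable to our own study". The figures show how precise the proposed analysis would be. They do not measure harm from leaving it out.

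**The case against.** The strongest reply is that the plan is silent, not deficient. Descriptive statistics can include differences and intervals, and nothing in Statistical analysis rules them out. It names no interval for the primary comparison either, so this is its general level of detail. Description is also a defensible choice for non-randomised factors that the trial was not sized for. The word *relationships* in Statistical analysis is already suitably cautious. Most of this stands. It is why the point is that no difference or interval is *specified*. A reader might infer that the plan excludes any estimate of uncertainty, but the text does not support that.

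A second reply concerns the score. Change is a natural reading, because the primary outcome in the sentence before is change and the abstract says that both surveys are collected so that changes can be calculated. No test or success criterion hangs on these factors, and tables could show all three scores together. This also stands in part: the room for selective reporting is real but small. A reader might infer that the plan opens the way to a false positive claim, but it attaches no claim of success to these factors.

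Neither reply settles whether association or effect modification is meant, nor gives the declared outcome a defined estimate.

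**Conclusion.** The point holds in a limited form. Three student factors are declared as secondary outcomes, and their only assigned analysis is descriptive. No between-level difference or interval is specified, the score is not named, and the question is ambiguous. The conclusion rests on the text and not on a calculation. The half-widths of about 0.11 to 0.14 for change are illustrations that assume two-level factors, 60:40 to 80:20 splits, 220 students and SD 0.42.

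A reader might go on to doubt the trial's main result. The documents give no ground for that here: the primary comparison between arms does not use these factors. This is a minor improvement that is worth making because it is cheap.

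**What to change.** In Statistical analysis:

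- Name the score, for example change in PPOS-D12, to match the primary outcome.
- State whether the question is association or modification of the intervention effect, and how each factor is coded. For example, say whether illness in the student and illness in a relative or friend count as one factor or more.
- For association, report for each factor the mean difference in change with a 95% CI, from a linear regression that includes trial arm.
- If effect modification is meant, report the factor-by-arm interaction with a 95% CI instead.
- Label the results exploratory and keep the descriptive tables alongside.

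In the abstract and Outcome measures, describe the results as associations, since the factors are not randomised, and give the same list of factors in both places.

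The cost is a few sentences and a small amount of extra analysis. No new data are needed, because the factors are already on the baseline questionnaire. The downside is several unpowered contrasts with possibly wide intervals, especially for interactions, which is why the exploratory label matters.

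### The between-arm analysis of the primary outcome is not tied to change and takes no account of baseline; a baseline-adjusted comparison should be named as primary

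*Combined protocol and SAP*

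**What the plan says.** Outcome measures defines the primary outcome as change: "The primary outcome measure will be the change in students' PPOS-D12 scores from baseline" to the end of the attachment.

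Statistical analysis names two comparisons of students' scores that bear on it. "Mean pre- and post-test PPOS scores will be compared using paired" *t* tests, and "Differences between PPOS scores in the intervention and control groups will be examined with unpaired" *t* tests. Neither is called primary. The first is not said to be run by arm. The second does not say which scores are meant. No confidence interval or baseline adjustment is mentioned.

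The abstract has the same looseness: students are surveyed twice "so that changes in their scores can be calculated, and the mean scores of the two groups compared".

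The sample size paragraph is clearer about what is being compared. It is "based on reported mean reduction of 0.11 in the PPOS score over one year in a group without any intervention", set against "a mean increase of 0.05 in the intervention group", and continues: "We therefore assumed a mean difference 0.16, with a standard deviation of 0.42". The SD of 0.42 equals the SD of change reported in the Background for the resident cohort. The design target is therefore a between-arm difference in change.

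**The concern.** The outcome definition and the sample size point to change, while the sentence describing the between-arm test refers only to scores. The sentence that follows it, on the nested study, does speak of changes in students' scores, so the authors make the distinction elsewhere. An analyst could follow the plan to the letter and compare end-of-year scores, or compare changes, and could choose after seeing the data. The two analyses have different precision, and only the second matches the SD used to size the trial.

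The paired tests do not fill the gap. A pre/post comparison, by arm or pooled, reflects a year of curriculum, maturation and repeat testing as well as the intervention, and makes no use of randomisation.

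Neither *t* test on its own makes the best use of the baseline PPOS-D12 score, which will already have been collected.

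**Working it through.** **Inputs.** Difference 0.16, change SD 0.42, 110 per arm, 5% significance, 90% power (Statistical analysis). Resident cohort: SD 0.48 at the start of the year, 0.51 at the end, 0.42 for change (Background). I take the test as two-sided, since the plan does not say. Randomisation makes the expected baseline difference zero, so 0.16 is also the expected difference in end-of-year scores.

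**The plan's own figure.** For a two-sample comparison, n per arm = 2 × [0.42 × (1.960 + 1.282) / 0.16]² = 144.8, or 145 per arm (290 in total) for 90% power. The stated 110 per arm does not reproduce at 90%. It corresponds to about 80%, for which the same formula gives 109 per arm. That is a separate point. It matters here only because the reference power for a test on change is 80%.

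**Implied pre-post correlation.**
r = (0.48² + 0.51² − 0.42²) / (2 × 0.48 × 0.51) = 0.3141 / 0.4896 = 0.64.

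**SD relevant to each analysis.**
- End-of-year score: 0.51.
- Change: 0.42.
- End-of-year score adjusted for baseline: 0.51 × √(1 − 0.6415²) = 0.391.

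**Power at 110 per arm.** Standard error = SD × √(2/110); power is from the noncentral *t*. The one degree of freedom spent on the baseline term is ignored.

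| Analysis | SD | SE | 0.16 / SE | Power |
|---|---|---|---|---|
| End-of-year score | 0.51 | 0.0688 | 2.33 | 64% |
| Change | 0.42 | 0.0566 | 2.83 | 80% |
| Baseline-adjusted | 0.391 | 0.0528 | 3.03 | 86% |

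**Sensitivity to the correlation.** Hold the change SD at 0.42 and let the pre and post SDs be equal. The end-of-year SD is then 0.42 / √(2(1 − r)) and the adjusted SD is 0.42 × √((1 + r)/2).

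| r | End-of-year SD | Adjusted SD | Power, end score | Power, change | Power, adjusted |
|---|---|---|---|---|---|
| 0.3 | 0.355 | 0.339 | 91% | 80% | 94% |
| 0.5 | 0.420 | 0.364 | 80% | 80% | 90% |
| 0.6 | 0.470 | 0.376 | 71% | 80% | 88% |
| 0.7 | 0.542 | 0.387 | 59% | 80% | 86% |
| 0.8 | 0.664 | 0.398 | 43% | 80% | 84% |

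Adjustment beats both *t* tests at every value shown. Which *t* test is better depends on whether r is above or below 0.5.

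**A conditional check on the paired tests.** Suppose they were run by arm and their p-values contrasted, with no true difference between arms, 110 per arm and change SD 0.42. At a shared change of −0.11, each paired test is significant with probability p = 0.777. The pattern in which controls fall significantly and intervention students do not then has probability p(1 − p) = 0.777 × 0.223 = 17%. With no change in either arm, p = 0.05. A pattern favouring the intervention (a significant fall in controls only, or a significant rise in intervention students only) has probability 0.05 × 0.95, about 5%. A two-sided 5% between-arm test favours the intervention falsely in 2.5%.

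**The case against.** A reader might infer that the plan tests change only within arms and deliberately excludes it from the between-arm comparison. The documents do not support that. An unpaired between-arm test is planned, change is the primary outcome, and the sample size is built on a difference in change. Reading the unpaired test as a test of change is consistent with all of this and may well be what was meant. The wording is open; it is not an exclusion.

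A reader might also infer that an effect will be claimed when one arm's paired test is significant and the other's is not. Nothing in the documents says so, or says that the paired tests are run by arm. If they are pooled, there is no pair of p-values to contrast. The 17% above is therefore the error rate of a misreading that the plan leaves open, not of the planned analysis.

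An unpaired test on end-of-year scores would still be a valid randomised comparison with 5% type I error, and one on change is valid too. The loss of power on end scores is not certain either. The SDs come from resident physicians, and the Limitations section concedes that published data may not be comparable. The Background also quotes first-year dental students with SDs of 0.33 before and 0.19 after their course. At those SDs an end-score test of 0.16 would have about 95% and over 99% power.

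All of this stands, and it limits the point to unclear specification and avoidable inefficiency. It does not remove the point: the plan still does not say which analysis answers the primary question.

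**Conclusion.** The concern holds as a gap in specification with a cost in efficiency. The only between-arm analysis named is an unadjusted *t* test on scores of an unstated kind, for a primary outcome defined as change. On the resident-cohort SDs, the choice moves power for a 0.16 difference at 110 per arm from about 64% (end scores) through 80% (change) to 86% (baseline-adjusted). These figures assume that those SDs carry over to Bern first-year students. Over correlations of 0.3 to 0.8, with equal pre and post SDs and change SD 0.42, end-score power spans about 91% to 43% and adjusted power about 94% to 84%. The ranking of the two *t* tests is uncertain, but the advantage of adjustment is not in doubt anywhere in that range. This supports a clarifying change that should be made; it is not evidence that the planned comparison is invalid.

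**What to change.** In Statistical analysis, name a single primary analysis: the between-arm difference in end-of-year PPOS-D12 score from a linear model with arm and baseline PPOS-D12 score as terms, reported with its 95% CI. State that the trial's conclusion about the intervention rests on this contrast alone. The unadjusted difference in mean change can be kept as a secondary presentation, since it corresponds directly to the sample size assumptions. Report mean pre/post change within each arm with confidence intervals as description, and drop the paired tests or state that no inference about the intervention will be drawn from them. Bring the abstract sentence into line.

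The cost is a few sentences, settled before the end-of-year scores are analysed. Both scores are already collected and linked under the plan, so no new data are needed.
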